5.1 SCREENING EXAMINATION AND ELIGIBILITY SCREENING FORM

All legal guardians/subjects must sign and date the most current IRB/IEC-approved written informed consent/assent (where appropriate) before any study-specific assessments or procedures are performed.

The assessments in [Table 5](#) should be obtained within a period of no more than 35 days before the subject is randomized, except as noted. *Extensions to the screening period of up to 7 days may be permitted under exceptional circumstances if certain results concerning eligibility are not available within the 35 days and only upon approval from the Medical Monitor.* Subjects must fulfill all the entry criteria for participation in the study (see Sections [4.2](#) to [4.4](#)). An Eligibility Screening Form documenting the investigator's assessment of each screened subject with regard to the protocol's inclusion and exclusion criteria is to be completed by the investigator. A screen failure log must be maintained by the investigator.

If a subject fails any laboratory Inclusion/Exclusion criteria at screening, the investigator may repeat the test twice within the screening period. This will not be considered as re-screening; see below. If the subject fails the laboratory criteria on the third assessment, he or she will not be able to enter the study. It will not be considered a retesting if blood samples have to be redrawn because of sample handling problems, breakage or sample integrity.

Subjects who fail to meet the entry criteria may be re-screened on one more occasion provided that enrollment remains open *and upon approval from the Medical Monitor.* *If re-screening is required, then the complete screening module should be repeated (except for those parameters indicated in [Table 5](#)). Re-screening is required if a subject has not met all of the eligibility criteria within 35 days from the original screening visit. It will not be considered a re-screening if blood samples have to be redrawn because of sample handling problems, breakage, or sample integrity.*

Table 5 Screening Assessments

Medical history and physical examination	Includes family history of HBV, concomitant medication (including for CHB), surgeries/procedures , and vital signs (blood pressure, heart rate, temperature).
Ophthalmological examination ^a	Within 6 months prior to baseline; repeat at screening only if any change in medical condition. By ophthalmologist (pediatric ophthalmologist is recommended) and including fundoscopic examination with dilation , visual acuity assessment, visual field testing (confrontation test is recommended for younger children), and color visual testing. Any subject who develops ocular symptoms should receive a prompt eye examination by an ophthalmologist and additional examinations as necessary.
Neuro-psychiatric Questionnaire	Children's Depression Inventory (CDI)
Growth	Weight and height

Ultrasound ^a	Within 6 months prior to baseline; repeat at screening only if any change in medical condition. To rule out hepatocellular carcinoma. Further liver imaging assessment may be performed if necessary.
Liver biopsy	Only if no previous histology available within 2 years prior to baseline or within 9 months prior to baseline for subjects with advanced fibrosis.
Liver elastography	For subjects taking part in site specific liver elasticity sub-study only
HCG pregnancy test ^b	For females of childbearing potential, a negative urine or serum HCG test needs to be documented within 24 hours prior to baseline. Note that the test may be performed at the baseline visit, provided that the result is available prior to randomization and commencement of treatment.
Hematology ^c	Complete blood count (hemoglobin, hematocrit, total white blood cell [WBC] count, differential WBC count [neutrophils, lymphocytes, monocytes, eosinophils, basophils]), platelet count, international normalized ratio (INR)
Clinical chemistry ^c	ALT, AST, GGT, total bilirubin, alkaline phosphatase, total protein, albumin, blood urea nitrogen (BUN)/urea, creatinine ^e , uric acid, total calcium, phosphorus, cholesterol, triglycerides, random glucose, sodium, chloride, potassium
Urinalysis ^b	Dipstick with subsequent microscopic evaluation if positive for blood
Immunology and special chemistry ^{a,d}	Alfa-fetoprotein, ceruloplasmin, A1AT, anti-mitochondrial antibody (AMA), ANA, anti-smooth muscle antibody (ASMA), anti-liver-kidney microsome-1 antibody (ALKM1), anti-HAV IgM, anti-HCV, anti-HIV, anti-HDV
HBV serology and virology ^{a,d}	HBeAg, anti-HBe, HBsAg, anti-HBs, quantitative HBsAg and HBeAg, HBV-DNA, HBV genotype
Thyroid function tests ^{a,d}	FT3, FT4, TSH, TPO antibodies, TBG

^a Parameter does not need to be repeated at re-screening if performed within 6 months prior to baseline, unless dictated by a change in the subject's medical condition or the parameter accounted for the original screen failure.

^b To be performed by local laboratory.

^c To be performed by a local laboratory in countries activated prior to April 2013, and by a central laboratory in countries activated after April 2013.

^d To be performed by central laboratory.

^e Estimated creatinine clearance will be calculated internally at baseline/switch baseline.

5.2 PROCEDURES FOR ENROLLMENT OF ELIGIBLE SUBJECTS

A subject will be enrolled in the study and assigned a screening number after the subject has given informed consent/assent. Once a subject has fulfilled the entry criteria they may be randomized or assigned, as applicable. Upon contacting IXRS, the investigator or designee must confirm/provide the following:

- Whether the subject has advanced fibrosis
- The subject's height and weight

- If the site is taking part in either the PK sub-study or the liver elastography sub-study, whether the subject will take part in these sub-studies

Advanced fibrotic subjects will be assigned to Group C. Non-advanced fibrotic/non-cirrhotic subjects will be randomized to Group A or Group B and stratified by genotype and ALT. Based on the height and weight provided, IXRS will confirm the dose for treated subjects.

In accordance with a request from the China Food and Drug Administration Clinical Trial Permit (CTP File No: 2013L00401), at sites in China only, this study will start with enrolling older pediatric patients first (aged 7 to <18 years old at baseline) in order to assess safety in this population before extending enrollment to younger patients. A Data Safety Monitoring Board (DSMB) will review the safety data from older pediatric patients enrolled in China together with all other available safety data from pediatric patients enrolled in rest of world, to support appropriate subsequent enrollment of the younger age group in China. The recruitment of younger patients at sites in China will only start if review of the data by the DSMB determines that there are no safety concerns.

The enrollment of subjects in the rest of world will remain unchanged; patients aged 3 to <18 years old at baseline will be enrolled. During study conduct, the Sponsor may postpone or stop the enrollment of subjects in certain age ranges in order to *ensure that a broad age distribution and representative dosing categories have been adequately studied.*

The subject randomization numbers will be generated by Roche or its designee and incorporated into a set of subject numbers and associated study group which will be given to the investigator over the telephone at the time of individual subject enrollment.

The investigator or designee will use the eCRF with the assigned subject number and enter the corresponding number for allocation to the study groups in the appropriate place on each subject's eCRF.

The subject randomization numbers are to be allocated sequentially in the order in which the subjects are enrolled according to the specification document agreed with the external randomization company/center. A subject Enrollment and Identification Code List must be maintained by the investigator.

5.3 CLINICAL ASSESSMENTS AND PROCEDURES

A baseline visit will be performed, and for subjects in Group A and Group C all baseline assessments and procedures must occur prior to administration of the first dose of PEG-IFN. *The first dose of PEG-IFN should be administered at the baseline visit.* Subjects will subsequently be seen for evaluation at the following timepoints:

Group A and Group C

- During treatment period: Weeks 1, 2, 4, 8, 12, 18, 24, 30, 36, 42, and 48

Pegylated Interferon alfa-2a—F. Hoffmann-La Roche Ltd
Protocol YV25718, Version E

69

- During initial 24 weeks of follow-up: follow-up Weeks 4, 12, and 24 post-*end of treatment*
- During extended long-term follow-up: Years 1, 1.5, 2, 3, 4, and 5 post-*end of treatment*

Group B—Non-Switch

- During principal observation period: Weeks 12, 24, 36, and 48
- During initial 24 weeks of follow-up: follow-up Weeks 12 and 24 post-principal observation period
- During extended long-term follow-up: Years 1, 1.5, 2, 3, 4, and 5 post-principal observation period

Group B—Switch

- During principal observation period: Weeks 12, 24, 36, and 48*
- During initial 24 weeks of follow-up: follow-up Weeks 12* and 24* post-principal observation period
- During extended long-term follow-up: Year 1* post-principal observation period
- During switch treatment period: Weeks 1, 2, 4, 8, 12, 18, 24, 30, 36, 42, and 48
- During initial 24 weeks of switch follow-up: switch follow-up Weeks 4, 12, and 24 post- *end of treatment* period
- During extended long-term switch follow-up: Years 1, 1.5, 2, 3, 4, and 5 post- *end of treatment* period

*Subjects may switch at any time between Week 48 and 1 year following Week 48. Switch baseline will take place at the time of the final visit of the pre-switch schedule. Results from all switch baseline assessments must be available and subjects must meet all switch criteria prior to commencing PEG-IFN.

The extended long-term follow-up visit at Year 1.5 will be by telephone.

For assessments and procedures required at each visit refer to [Table 2](#) to [Table 4](#).

For visits up to and including Week 48, the visit window is ± 3 days.

For visits after Week 48 and up to and including follow-up Week 24, the visit window is ± 7 days.

For visits after follow-up Week 24, the visit window is ± 28 days.

Any subject who discontinues study treatment should return to complete assessments as per the Week 48/Switch Week 48 visit and enter the post-*end of treatment* follow-up period (see Section [4.6.1](#)).

5.3.1 Efficacy

5.3.1.1 Main Efficacy Assessments

Efficacy (see Section 8.1 for primary and secondary endpoints) will be determined from assessment of HBeAg and HBsAg seroconversion, loss of HBeAg and HBsAg, HBV-DNA, and ALT (see Section 5.4 for laboratory assessment details).

5.3.1.2 Liver Elasticity

At least 50 consenting/assenting subjects at specific sites will take part in a liver elasticity sub-study. For these subjects, liver elastography will be performed at baseline, end of treatment/principal observation period, follow-up Week 24, and follow-up Year 2.

Change in the LSM over time will be assessed comparing treated and untreated subjects.

Baseline liver elasticity will also be explored for association with the screening liver biopsy result in these sub-study subjects.

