8.1.2 Secondary Endpoints

- Loss of HBeAg, HBsAg seroconversion (loss of HBsAg and presence of anti-HBs), loss of HBsAg, quantitative serum ALT, proportion of normal ALT, quantitative HBV-DNA, suppression of HBV-DNA < 100,000 copies/mL (<20,000 IU/mL), < 10,000 copies/mL (<2,000 IU/mL), undetectable and change from baseline, combined endpoint of HBeAg seroconversion and HBV-DNA < 100,000 copies/mL (<20,000 IU/mL), and combined endpoint of HBeAg seroconversion and HBV-DNA <10,000 copies/mL (<2,000 IU/mL) at the end of treatment/principal observation period, 24 weeks after end of treatment/principal observation period, and 1, 2, 3, 4 and 5 years after end of treatment/principal observation period.
- Persistence of HBeAg seroconversion (loss of HBeAg and presence of anti-HBe) at the end of treatment/principal observation period, and 1, 2, 3, 4, and 5 years after end of treatment/principal observation period.
- Descriptive change from baseline in liver elasticity (for subjects enrolled in the liver elasticity sub-study) at the end of treatment/principal observation period, and 24 weeks and 2 years after end of treatment/principal observation period.

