8.2.5 Efficacy Analysis

The primary efficacy analysis will compare efficacy in Group A with Group B. The efficacy data of Group A and Group B will be qualitatively evaluated alongside subjects in Group C and the switch arm.

The primary analysis of the response rate variables will be with the Cochran-Mantel-Haenszel test (χ^2) stratified by genotype (with strata of A and non-A) and ALT ($<5 \times$ the ULN and $\geq 5 \times$ the ULN). Fisher's exact test will be used as a secondary analysis. The response rates for HBeAg seroconversion will be analyzed at the end of the initial 24-week follow-up period.

Several secondary analyses are planned. Descriptive statistics of secondary endpoints loss of HBeAg, HBsAg seroconversion, loss of HBsAg, proportion of normal serum ALT, suppression of HBV-DNA, and combined endpoints will be summarized by Groups A, B, and C separately. Exploratory p-values will be presented using Fisher's exact test.

Quantitative serum ALT and quantitative HBV-DNA will be summarized by timepoints numerically and graphically over time. No formal statistical tests are planned. Graphs of secondary endpoints and corresponding 95% confidence intervals over time by group will be displayed.

For subjects in the liver elasticity sub-study, LSM will be measured at baseline, end of treatment/principal observation period, and at 24 weeks and 2 years after the end of treatment to assess change in liver elasticity over time. These results in subjects receiving treatment (Group A) will be compared with parallel measurements in the untreated control arm (Group B). For the comparison with liver biopsy at baseline, associations with liver stiffness will be explored using liver biopsy fibrosis score. Continuous outcomes will be studied using Pearson correlation, and potential

categorizations will be investigated as well. Confidence intervals will be provided as needed. No formal statistical tests will be carried out.

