4. STATISTICAL METHODS

All analyses for comparing the PEG-IFN treatment (Group A) with untreated control (Group B) are presented in [Section 4.3](#) to [Section 4.6](#). Analyses for Group C and the Switch arm will be presented in [Section 4.7](#) and [Section 4.8](#) respectively.

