4.4.5 Liver Elasticity Sub-study

Liver elasticity analysis in this section will be performed on those patients enrolled in liver elasticity sub-study⁴. Liver elasticity analysis results will be separately displayed for those patients enrolled in liver elasticity sub-study.

Liver stiffness measure (LSM) and its change from baseline over time will be summarized by treatment group. Graphs of change from baselines of LSM and their corresponding 95% confidence intervals over time will be displayed by treatment group.

Baseline LSM will be summarized by baseline characteristics subgroups, including fibrosis stages, age groups (<12, ≥12) and BMI (<18.5, 18.5 ~ 24.9, >25.0). Box plots of baseline LSM will be displayed by various baseline characteristics subgroups above.

Baseline liver elasticity will also be explored for association with the screening liver biopsy result in these sub-study patients using liver biopsy fibrosis score, using Spearman's correlation coefficients. Confidence intervals of correlation coefficients will be provided as needed.

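### SAP 4.4.5 could report the Group A minus Group B difference in liver-stiffness change with its 95% CI, which the planned by-group intervals do not show

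*Protocol*

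**What the plan says.** Protocol 5.3.1.2 gives the sub-study a comparative purpose: "Change in the LSM over time will be assessed comparing treated and untreated subjects". Protocol 8.2.5 says the Group A results "will be compared with parallel measurements in the untreated control arm (Group B"). The same paragraph ends: "No formal statistical tests will be carried out". Protocol 8.1.2 lists the change in liver elasticity among the secondary endpoints and labels it descriptive.

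SAP Section 4 opens by saying where the comparisons are: "All analyses for comparing the PEG-IFN treatment (Group A) with untreated control (Group B) are presented in" Sections 4.3 to 4.6. Section 4.4.5 lies in that range. For change in LSM it specifies two things:

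- A numerical summary: "Liver stiffness measure (LSM) and its change from baseline over time will be summarized by treatment group".
- Plots of that change against time, in which each group carries its own 95% interval.

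The rest of 4.4.5 concerns baseline LSM: summaries and box plots by subgroup, and a Spearman correlation with the biopsy fibrosis score. Neither document specifies a between-group difference in LSM change, an interval for such a difference, or a model that uses baseline LSM.

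The sub-study is to have at least 50 children (Protocol 5.3.1.2; SAP 4.4.5, footnote). No power or precision basis is given for that number.

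**The concern.** The protocol asks how LSM change differs between treated and untreated children. The SAP describes each group in turn and leaves the contrast to the reader. The interval that goes with the question is the one for the difference, and it cannot be read directly from two separate intervals.

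What is at stake is modest. A reader of the report would see two curves with error bars and would not be told how large an A minus B difference the data support or exclude. The baseline scan, scheduled for each Group A and Group B sub-study child, would be used only through subtraction. An unadjusted difference could be worked out afterwards from the group means, SDs and numbers. A baseline-adjusted one could not.

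**Working it through.** **No stated figure to reproduce.** The sub-study's minimum of 50 has no derivation. The main trial's 145 is a calculation for the seroconversion endpoint and plays no part here.

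**Inputs.**
- Sub-study size: 50, the stated minimum (Protocol 5.3.1.2).
- Allocation: 2:1, A to B (Protocol 3.1). Applied to 50, this gives about 33 v 17.
- Assumed: all 50 are in Groups A and B, the 2:1 ratio holds within the sub-study, none are missing, and the SD of LSM change is the same in both groups.
- Not given in the documents: the SD of LSM, and the correlation r between baseline and follow-up LSM. Results are therefore in SD units, over r = 0.3 to 0.8.

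**Step 1: the planned intervals against the interval for the comparison** (units: SD of change).
- Group A: t(32 df)/√33 = 2.037/5.745 = 0.35.
- Group B: t(16 df)/√17 = 2.120/4.123 = 0.51.
- Difference A − B: t(48 df) × √(1/33 + 1/17) = 2.011 × 0.2985 = 0.60.

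The interval for the difference is wider than either displayed interval, so neither one gives the precision of the comparison.

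**Step 2: what baseline adjustment adds.** Let the cross-sectional LSM variance be σ², equal at baseline and follow-up. The change score has variance 2σ²(1 − r). The ANCOVA residual variance is σ²(1 − r²). Their ratio is (1 − r²)/[2(1 − r)] = (1 + r)/2, so the standard error is multiplied by √[(1 + r)/2].

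| Assumed r | SE multiplier | SE reduction | Half-width, change score (σ) | Half-width, ANCOVA (σ) |
|---|---|---|---|---|
| 0.3 | 0.81 | 19% | 0.71 | 0.57 |
| 0.5 | 0.87 | 13% | 0.60 | 0.52 |
| 0.7 | 0.92 | 8% | 0.47 | 0.43 |
| 0.8 | 0.95 | 5% | 0.38 | 0.36 |

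The half-widths are for the A − B difference at 33 v 17, in units of the cross-sectional SD. With 20% of children missing (27 v 13, also an assumption), the ANCOVA half-widths become 0.65, 0.59, 0.49 and 0.41.

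**Step 3: which visits give a treated-versus-untreated contrast.** Protocol Table 3 schedules Group B elastography at baseline, Week 48, follow-up Week 24 and Year 2. Switching is open from Week 48 until one year later, and the switch baseline takes place at the final pre-switch visit (Protocol 5.3). The Week 48 scan therefore precedes any switch. By the later visits some Group B children may have started PEG-IFN, and SAP 4.4.5 has no rule for them.

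**The case against.** The strongest reply is that the plan does what it says. The endpoint is labelled descriptive, formal tests are ruled out, and side-by-side summaries with intervals are a natural reading of a descriptive comparison. By-group display is also the plan's convention for continuous endpoints: Protocol 8.2.5 handles quantitative ALT and HBV-DNA this way, and SAP 4.4.2 does so for all continuous secondary endpoints. The LSM change is tabulated as well as plotted, so the reader is not confined to graphs. Table layouts are left to DAP Module 2 (SAP Section 1), which is not available here and might include a difference.

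Most of this stands, and it rules out three stronger readings that a reader might infer.

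- **That the SAP breaks a commitment, or that the sub-study cannot answer its question.** The documents do not support this. Comparing groups descriptively does not promise an estimated contrast, and an unadjusted difference can be derived from the planned summaries.
- **That baseline adjustment was promised and left out.** Neither document mentions it for LSM. ANCOVA is a recommendation on efficiency. The planned change from baseline already uses each child's baseline value, and the further gain depends on an r that the documents do not give.
- **That conclusions will be drawn from whether the two intervals overlap.** No document proposes such a rule.

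The reply does not show that the by-group intervals carry the precision of the comparison. Nor does the exclusion of tests stand in the way, because a difference with a 95% CI and no p-value is an estimate. The method for that estimate belongs in the SAP even if the layout sits elsewhere.

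**Conclusion.** The point holds as a low-severity free improvement, not as an error. The protocol sets a Group A versus Group B comparison of LSM change. The SAP section meant to contain it plans only by-group summaries and intervals, with half-widths of about 0.35 and 0.51 SD of change where the comparison has 0.60.

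Those figures rest on 33 v 17, equal SDs, no Group C children and no missing scans. The gain from baseline adjustment, about 19% down to 5% of the standard error for r from 0.3 to 0.8, rests on equal baseline and follow-up variances and on an assumed correlation. The sub-study is site-specific and unpowered, and nothing here touches the primary analysis.

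**What to change.** In SAP 4.4.5, for the randomized Group A and Group B sub-study children:

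- Add the A minus B difference in LSM change from baseline with its 95% CI, from an ANCOVA with baseline LSM as covariate. Give no p-value.
- Report it at Week 48, which precedes any switch.
- At follow-up Week 24 and Year 2, identify the Group B children who have switched, so that they are not read as untreated.
- Keep the by-group summaries and graphs as planned. Group C stays separate, as Protocol 3.1.1.2 and SAP 4.7 already have it.

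The cost is a sentence or two in the SAP and an added table row. No new data are needed. Nor is a protocol amendment, since Protocol 8.2.5 already states the comparison and no test is added.

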5.3.2 Safety

Safety assessments will include symptom directed physical examination, vital signs, growth, neuro-psychiatric questionnaire (PEG-IFN-treated subjects only, post-baseline), review of concomitant medications, reported AEs and specified safety laboratory assessments of hematology, clinical chemistry, thyroid function, and urinalysis. Additional safety assessments will be determined from tabulations of dose adjustments and premature withdrawals from treatment for safety or tolerability reasons.

All subjects need to have an ophthalmological examination (*consisting of fundoscopic examination with dilation, visual acuity assessment, visual field testing (confrontation test is recommended for younger children), and color visual testing*) by an ophthalmologist (*pediatric ophthalmologist is recommended*) within 6 months prior to baseline. *During the study*, subjects treated with PEG-IFN will receive *additional* ophthalmological examination as per the schedules in Table 2 and Table 4. Any subject who develops ocular symptoms should receive a prompt eye examination by an ophthalmologist and additional examinations as necessary.

For females of childbearing potential, a pregnancy test will be performed within 24 hours prior to baseline or switch baseline. This could be performed at the baseline visit, provided that the result is available prior to randomization and commencement of treatment. Pregnancy testing will also be performed at any time secondary amenorrhea of more than 1 week occurs. In addition, subjects treated with PEG-IFN will have pregnancy tests performed as per the schedules in Table 2 and Table 4.

Measurements of growth must be taken using the same instruments in the same individual. A stadiometer with mean of three readings should be used for height measurement. For Group A and C subjects, at Weeks 12, 24, and 36, and for switch subjects at switch baseline, switch week (SW)12, SW24, and SW36 the investigator or

designee will provide IXRS with the subject's height and weight so that the BSA and dose can be provided.

Height will be collected from consenting biological parents. This information may be entered directly onto the eCRF and the eCRF may be considered as the source document.

During the extended long-term follow-up period, only the following safety data will be collected:

- Persisting AEs initially reported prior to follow-up Week 24 (including neurological and psychiatric events)
- New-onset SAEs (including neuro-psychiatric events) and non-serious AEs of special interest related to PEG-IFN
- Deaths
- Growth: weight and height
- Thyroid function

